7.8 Concomitant Medications

Prior or current use of antibodies/Fab fragments from sheep (e.g. Digibind[®], DigiFab[®], CroFab[®]), digoxin, or other digitalis-like products is prohibited.

Routine medications such as those directly related to analgesia pre-delivery, epidural or other regional or local anesthesia, or general anesthesia, will be collected via checklist as noted in [Appendix 8](#). Maternal concomitant medications not identified in Appendix 8 that have been taken within 28 days of screen and during the course of the study will be recorded in the CRF.

For infants, routine concomitant medications as noted in [Appendix 8](#) will be captured via checklist. Infant concomitant medications not identified in Appendix 8 that are taken between birth and 36 weeks corrected gestational age will be recorded in the CRF.

7.9 Total Volume of Maternal Blood Collected

Up to eleven 6 mL blood samples will be collected for a total of 66 mL of blood collected per subject for AMAG-423 pharmacokinetic analysis.

Approximately 12 mL of blood will be collected at Screening, 12 mL per day for Days 2-5 and 12 mL each at 24 hours post final dose, 24 hours postpartum, up to 24 hours prior to discharge, and 6 weeks postpartum for a total of up to 108 mL of blood collected per subject for clinical laboratory assessments.

Approximately 6 mL of blood will be collected at Screening and 6 weeks postpartum for immunogenicity analysis.

In addition, two 6 mL blood samples will be collected for a total of 12 mL of blood collected per subject for assay development.

The total volume of blood collected from each subject over the entire study will be approximately 198 mL.

7.10 Total Volume of Infant Blood Collected

At the time of delivery, approximately 2 mL of cord blood, if available, will be collected for analysis of arterial cord gas pH and base excess/base deficit and AMAG-423 concentration.

At 36 weeks (\pm 1 week) corrected gestational age, approximately 0.5 mL of blood will be collected for immunogenicity analysis.

8 ASSESSMENT OF SAFETY

8.1 Overview of Safety Monitoring

It is the responsibility of the Principal Investigator to oversee the safety of the subject at his/her site and to report all AEs/SAEs that are observed or reported during the study, regardless of relationship to study drug or clinical significance.

The Medical Monitor has medical authority for the evaluation of the safety aspects of this clinical study. The Investigator may contact the Medical Monitor with specific medical questions on the study protocol, subject's eligibility, as well as AEs.

8.2 Safety Assessments

Safety assessments for the mother and fetus/infant will be collected.

Maternal assessments will include vital signs (blood pressure, heart rate, respiratory rate, body temperature, and pulse oximetry), body weight, mental status exams, physical examinations, clinical laboratory tests (chemistry, hematology, and urinalysis), immunogenicity analyses, MEOWS, preeclampsia symptom assessment, and adverse events. The schedule of these safety assessments has been discussed in the Study Procedures section above and is provided in [Appendix 1](#).

Fetal/infant assessments will include fetal heart tracing, biophysical profile (fetal breathing movements, gross body movements, tone, reactive heart rate and qualitative amniotic fluid), infant outcome assessment, cord blood assessment if available (arterial cord gas pH and base excess/base deficit), cranial ultrasound, infant exam (weight, length, and head circumference), immunogenicity analysis, and adverse events.

For study purposes, standard of care assessments (e.g., ECG, infant labs) will not be captured unless there are clinical findings, at which point they will be captured as adverse events.

8.2.1 Vital Signs

Vital signs (i.e., blood pressure, heart rate, respiratory rate, body temperature, and pulse oximetry) will be obtained at Screen, during the treatment period, and during the follow-up period. During the treatment period a full set of vital signs will be obtained every 4-6 hours, as much as possible. During the follow-up period, vital signs will be collected 24 hours after the final dose and then once a day until discharge and at the 6-week postpartum visit (in the morning, when possible).

For ambulatory subjects, vital signs should be measured after approximately 5 minutes of quiet rest with the subject comfortably seated, legs uncrossed, back and arm supported with the middle of the cuff on the upper arm. For non-ambulatory subjects, vital signs should be measured in a semi-reclined position.

8.2.2 Physical Examinations and Mental Status Examination

A physical examination and a mental status examination will be performed at Screen. During the treatment period and during the follow-up period, a mental status examination and brief physical exam (heart and lung assessment, deep tendon reflex assessment, and clonus assessment) will be completed. During the treatment period, exams will be conducted per standard of care, and/or minimally, once a day, starting approximately 24 hours after the first dose. As much as possible,

mental status exams and brief physical exams should be completed 24 hours apart. During the follow-up period exams will be conducted per standard of care, and/or minimally, 24 hours after final dose (± 4 hours), 24 hours postpartum (± 6 hours), up to 24 hours prior to discharge, and at the 6-week postpartum visit (if available).

Any new clinically significant abnormalities occurring after Screening should be reported as adverse events.

8.2.3 Height and Weight Measurements

Height will be measured at Screen only; weight will be measured at Screen and during the follow-up period. During the treatment period weight will be collected per standard of care. During the follow-up period weight will be collected per standard of care, and/or minimally, 6 hours (± 2 hours) post final dose, 24 hours postpartum (± 6 hours), up to 24 hours prior to discharge, and at the 6-week postpartum visit (if available).

8.3 Clinical Laboratory Assessments

Clinical laboratory assessments (chemistry, hematology, urinalysis – see [Appendix 3](#)) will be performed at Screen and during the treatment and follow-up periods. During the treatment period, clinical labs will be collected 24 hours after the first dose (± 2 hours) and then per standard of care and/or minimally, once a day. As much as possible, labs should be collected 24 hours apart. During the follow-up period, clinical labs will be collected per standard of care and/or minimally, 24 hours post final dose (± 4 hours), 24 hours postpartum (± 6 hours), up to 24 hours prior to discharge, and at the 6-week postpartum visit (if available).

Any new clinically significant abnormal results occurring after Screening should be reported as adverse events.

8.4 Preeclampsia Symptom Assessment

Preeclampsia symptom assessment will be conducted at Screen and during the treatment and follow-up periods. During the treatment period preeclampsia symptom assessment will be conducted per standard of care, and/or minimally, once a day, starting approximately 24 hours after the first dose. During the follow-up period preeclampsia symptom assessment will be conducted per standard of care, and/or minimally, once a day until discharge and at the 6-week postpartum visit (or by phone if unable to come to clinic for visit).

8.5 Modified Early Obstetric Warning Score (MEOWS)

Modified early obstetric warning score (MEOWS) (see [Appendix 5](#)) will be conducted at Screen and during the treatment and follow-up periods. During the treatment period MEOWS will be conducted 24 hours after the first dose (± 2 hours) and then, minimally, once a day. As much as possible, MEOWS should be collected 24 hours apart. During the follow-up period MEOWS will be conducted per standard of care, and/or minimally, 24 hours after final dose (± 4 hours), 24 hours postpartum (± 6 hours), up to 24 hours prior to discharge, and at the 6-week postpartum visit.

8.6 Immunogenicity Analysis

Blood samples will be collected for immunogenicity analysis of the mother at Screen and 6 weeks postpartum and for the infant at 36 weeks (± 1 week) corrected gestational age. Samples will be assayed for immune response against anti-AMAG-423 antibody concentration.

Immunogenicity blood samples will be prepared, stored and shipped to the bioanalytical laboratory for analysis according to immunogenicity sampling instructions that will be provided separately.

8.7 Fetal Heart Rate Monitoring and Biophysical Profile

Fetal heart rate monitoring will be conducted at Screen, and during the treatment period. During the treatment period, fetal heart rate monitoring will be performed continuously for 24 hours after the first dose (to be initiated at the start of the first dose), and for one hour after initiation of each dose during the remainder of the treatment period. During the follow-up period fetal heart rate monitoring will be conducted per standard of care. Clinically significant abnormal findings along with category designation (e.g., III) from fetal heart rate monitoring must be recorded.

If continuous fetal heart rate monitoring is difficult or not possible due to subject's weight and/or fetal gestational age, attempts to obtain several one hour strips on Day 1 of treatment should be made documenting why continuous fetal heart rate monitoring is not possible.

Biophysical profile (fetal breathing movements, gross body movements, tone, reactive heart rate and qualitative amniotic fluid) will be conducted at Screen, and per standard of care, and/or minimally, at 6 hours (± 2 hours) post final dose of study drug.

8.8 Infant Safety Assessments

The following assessments will be conducted for the infant (standard of care assessments will not be captured unless there are clinical findings):

- If cord blood is available, a cord blood sample will be collected for the following assessments:
 - Arterial cord gas pH and base excess/base deficit
 - Analysis of AMAG-423 concentration
- Infant physical examination and laboratory assessments (clinical chemistry and hematology) – standard of care until 36 weeks (± 1 week) corrected gestational age.
- Blood sample for immunogenicity analysis will be collected at 36 weeks (± 1 week) corrected gestational age.
- Infant cranial ultrasound – Day 7 (± 1 day) and at 36 weeks (± 1 week) corrected gestational age.
 - Cranial ultrasounds should be performed per existing medical practice imaging process standards. To ensure consistency of IVH grading, each site will digitally record the Day 7 and 36 weeks (± 1 week) corrected gestational age cranial ultrasounds for analysis by a central radiologist.
- Status at birth
 - Apgar scores at 1 and 5 minutes
 - Apgar score at 10 minutes, if available
- Infant exam (weight, length, head circumference)
- The infant outcome assessment will be completed at birth and at 36 weeks (± 1 week) corrected gestational age and will include:
 - NICU stay
 - Ventilator use and duration
 - CPAP / HFNC use and duration
 - Status at 36 weeks (± 1 week) corrected gestational age (i.e., alive or expired, hospitalized or discharged).

- Blood transfusion receipt and any available related information (e.g., hemoglobin and hematocrit levels prior to transfusion and within 24 hours of transfusion, and NPO status)
- Medical complications including:
 - PDA – documentation regarding details of PDA condition and treatment should also be captured.
 - Respiratory distress syndrome
 - NEC ([Appendix 6](#))
 - Retinopathy of prematurity, including stage
 - Bronchopulmonary dysplasia
 - Hypoxic ischemic encephalopathy
 - IVH, including grade ([Appendix 7](#))
 - Cystic periventricular leukomalacia
 - Sepsis, early and late onset
 - Previously unrecognized anomalies (e.g., including, but not limited to, ASD and VSD).
 - Other conditions of prematurity as outlined in [Appendix 4](#)

8.9 Adverse Events

An adverse event is defined as any untoward medical occurrence associated with use of a drug in humans, whether or not considered drug related. It can be any unfavorable and unintended sign (including laboratory values), symptom or disease temporally associated with use of the study treatment, whether or not it is associated with investigational treatment.

For purposes of this study, symptoms/sequelae of preeclampsia/eclampsia, symptoms of pregnancy and childbirth, and conditions related to prematurity are not considered adverse events unless they are unexpected or are significantly worse than would normally be expected ([Appendix 4](#)) in the opinion of the Investigator.

All AEs reported by the subject or observed will be recorded. Serious adverse events (SAEs) should be reported to the sponsor by telephone or fax within 24 hours of learning of their occurrence. Non-serious adverse event data will be recorded in each subject's CRF and submitted to the sponsor for review on an ongoing basis in conjunction with interim Sponsor monitoring visits.

Adverse event collection begins from the time of Informed Consent and continues throughout the study, until 6 weeks postpartum for the mother, and for the infant until 36 weeks (\pm 1 week) corrected gestational age. A separate AE record will be maintained for mothers and infants. Mothers will be questioned about their general health in conjunction with vital sign assessments. The question should be of a general nature and should not suggest symptoms to the subject (e.g., "How are you feeling?" rather than "Do you have a headache?"). If an AE is reported or observed, the site staff should follow the initial question with clinical evaluations and additional questions aimed at obtaining additional details about the AE.

When adverse events are observed or reported, whether in response to indirect questioning or volunteered by subjects, all relevant evaluations will be completed and appropriate treatment provided, if necessary. Subjects with adverse events should be followed until the Investigator and Sponsor consider the event to have resolved, stabilized, or no longer require follow-up for study purposes.

In order to avoid vague, ambiguous, or colloquial expressions, the adverse event should be recorded in the CRF using standard medical terminology rather than the subject's own words.

Whenever the Investigator is confident of a unifying diagnosis, all related signs, symptoms and abnormal test results should be grouped together, as a single AE (e.g., cough, rhinitis, and sneezing should be reported as “upper respiratory infection” if that is the diagnosis).

All adverse events are to be evaluated for intensity and causal relationship to the use of study drug as well as evaluated for seriousness. Grading of intensity and causality will use the following scales.

Intensity

- **Mild:** Usually transient, requires no special treatment, and does not interfere with the subject’s daily activities.
- **Moderate:** Usually causes a low degree of inconvenience or concern to the subject, and may interfere with daily activities, but usually is ameliorated by simple therapeutic measures.
- **Severe:** Significantly interferes with the performance of a subject’s usual daily activities, and generally requires systemic drug therapy or other treatment.

Causality

- **Probably not related to study drug:**
An event that is unlikely to have any relationship to the study drug even if such relationship cannot be definitely ruled out. This category should also be used for events that are known to be definitely unrelated to the study drug, e.g. events that occur after the subject has enrolled in a study but prior to study drug exposure.
- **Possibly related to study drug (i.e., suspected adverse reaction):**
An event that follows a reasonable temporal sequence from administration of the drug and where a causal relationship between drug administration and event is a reasonable possibility, even if the event could readily have been produced by a number of other factors. The expression “reasonable possibility” is meant to convey in general that there are facts (evidence) or arguments to suggest a causal relationship.
- **Probably related to study drug (i.e., adverse reaction):**
An event that (1) follows a reasonable temporal sequence from administration of the drug, (2) follows a known or expected response pattern to the suspected drug, (3) is confirmed by stopping or reducing the dosage of the drug, or (4) could not be more reasonably explained by the known characteristics of the subject’s clinical state.

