9.7 Analysis of Safety Data

Safety data as outlined in [Section 8](#) will be summarized by treatment group for both mothers and infants. Summary statistics will be prepared for measured values and changes from baseline values for each dose group. No statistical inference testing will be performed on the safety data.

Adverse events will be coded using the Medical Dictionary for Regulatory Activities (MedDRA) coding dictionary and summarized by relatedness, intensity, and seriousness. AEs may also be summarized by other factors such as gestational age or intensity of baseline preeclampsia symptoms. Summaries of the adverse event data will be completed for all subjects. Summaries of the number and percentage of subjects with at least one treatment emergent AE, classified according to preferred term and/or body system using the MedDRA dictionary, will be provided overall and by treatment group for:

- Overall summary
- All treatment-emergent AEs
- Treatment-emergent AEs by relationship (probably not related, possibly related, probably related)
- Treatment-emergent AEs by intensity (mild, moderate, severe)
- SAEs
- Treatment-emergent AEs leading to withdrawal from the study

Heart rate, systolic and diastolic blood pressure, temperature, respiratory rate, and pulse oximetry versus time data will be summarized by treatment group with descriptive statistics at each scheduled time point. Individual and mean values versus time profiles will be provided for each treatment group. Summaries of treatment-emergent clinically important abnormalities in vital sign and laboratory data will be provided. No inferential statistical analysis is planned.

Clinically significant new abnormal findings of vital signs or clinical laboratories will be reported as adverse events.

Laboratory parameters, vital sign data, and weight will be summarized by treatment group and presented in tabular and graphic formats where appropriate. Appropriate cross-tabulations will be provided to detect any significant changes in laboratory parameters, vital sign values, or weight but no formal statistical tests are planned.

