Appendix 8: Routine Maternal and Infant Concomitant Medications

Maternal Pre-Delivery:

- Analgesia pre-delivery (e.g., Fentanyl, Tylenol, Nubain/phenergan). Opioids should not be collected as a routine medication.
- Antacids/ Indigestion preparations (e.g., Tums, Pepcid, Zantac)
- Antiemetic (e.g., Compazine, Phenergan, Reglan, Zofran)
- Asthma inhaler or preventative treatment (e.g., Albuterol, Advair, Flovent)
- Epidural or other regional anesthesia
- General anesthesia
- Local anesthesia (pudendal block) for episiotomy
- Iron (Ferrous sulfate) for anemia prevention or treatment
- IV fluids, including use of lidocaine to start IV (e.g. D5W, NSS, Ringers lactate)
- Laxative/ stool softener/ other constipation treatment (e.g., Colace, Metamucil)
- Oxygen (via mask or nasal)

Maternal Post-Delivery:

- Analgesia post delivery (e.g., Fentanyl, Tylenol, Nubain/phenergan). Opioids should not be collected as a routine medication.
- Antacids/ Indigestion preparations (e.g., Tums, Pepcid, Zantac)
- Antiemetic (e.g., Compazine, Phenergan, Reglan, Zofran)
- Asthma inhaler or preventative treatment (e.g., Albuterol, Advair, Flovent)
- Birth control
- Hemorrhoid medication (e.g., Preparation H, Proctofoam, Tucks)
- Iron (Ferrous sulfate) for anemia prevention or treatment
- IV fluids (e.g. D5W, NSS, Ringers lactate)
- Injection for prevention of rhesus antibody formation, (e.g., Rhogam)
- Laxative/ stool softener/ other constipation treatment (e.g., Colace, Metamucil)
- Sitz bath

Infant:

- Antibiotic eye drops
- Vitamin D
- IV fluids
- Diuretics
- Vitamin A supplements
- Corticosteroids
- Prophylactic Vitamin K
- Systemic antibiotics
- Surfactant
- Iron supplements
- Bronchodilators
- Caffeine
- Retinopathy of prematurity exam medications (e.g., cyclopentolate, proparacaine)
- Total parenteral nutrition
- Calcium
- Multivitamin (with or without iron)

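### Section 8.9 grades fetal and infant adverse events on an intensity scale written for adults, so infant severity will be graded inconsistently

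*Combined protocol and SAP*

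**What the plan says.** Section 8.9 sets the rule: "All adverse events are to be evaluated for intensity and causal relationship to the use of study drug", and "Grading of intensity and causality will use the following scales". One intensity scale follows.

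- Mild: "Usually transient, requires no special treatment", and no interference with daily activities.
- Moderate: slight inconvenience or worry for the subject, possible interference with daily activities, and an event that "usually is ameliorated by simple therapeutic measures".
- Severe: significant interference with the subject's "usual daily activities, and generally requires systemic drug therapy or other treatment".

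The same section keeps a separate adverse-event record for infants, up to 36 weeks corrected gestational age. The schedule in Appendix 1 has a fetus/infant monitoring row that starts at screening. Section 9.7 states that safety data "will be summarized by treatment group for both mothers and infants", and its list of tables includes treatment-emergent events split by intensity, with no restriction to mothers. Neither a fetal or infant intensity scale nor any instruction for adapting the adult one appears in the text.

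Appendix 8 places "Systemic antibiotics" on the checklist of routine infant medication, along with caffeine, corticosteroids, diuretics and parenteral nutrition.

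**The concern.** The scale assumes a subject who goes about her day and can say how much an event bothers her. Fetuses and preterm infants in intensive care do neither, yet the rule covers them and the results are to be tabulated.

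Safety in the offspring is secondary objective 2, and the monitoring board in section 6.4.5 reviews adverse events. Under section 8.9 and Appendix 4, conditions of prematurity become adverse events only when the investigator finds them unexpected or clearly worse than usual. The infant events that do reach the table therefore include those where severity is most informative. Because section 9.7 plans no testing of safety data, the reader has only the descriptive categories to go on, and they need a common meaning across sites.

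**Working it through.** The documents state no figure on this point, so the check is a reading of the scale, level by level, as it would apply to a live-born preterm infant.

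| Level | Activity or subject-reported part | Treatment part | What an infant's grader can use |
|---|---|---|---|
| Mild | No interference with daily activities | No special treatment; usually transient | Treatment and duration |
| Moderate | Slight inconvenience or worry; possible interference | Simple measures usually suffice | Treatment only |
| Severe | Significant interference | Generally a systemic drug or other treatment | Treatment only, but the two parts are joined by *and* |

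**Step 1: literal reading.** Severe needs the activity part as well as the treatment part. An infant cannot meet the activity part, so no infant event can be severe, however grave.

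**Step 2: activity part dropped.** What remains is a ladder: no special treatment, simple measures, systemic drug or other treatment. Mild is still recognisable. The boundary between moderate and severe is not, because the severe wording admits any other treatment and the moderate wording does not say what is simple.

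**Step 3: an example.** Take an infant event treated with a systemic antibiotic. It is not mild, because it needed treatment. On the literal reading it is not severe. With the activity part dropped, it is severe if the systemic-drug wording decides, and moderate if the site regards a drug on the routine checklist in Appendix 8 as a simple measure. Nothing in section 8.9 settles the choice.

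**Step 4: fetal events.** The activity part has no meaning, and the scale does not say whether treating the mother, or delivering, counts as treatment of the fetal event. Neither part gives a clear grade.

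**Step 5: how many graders.** The synopsis plans about 200 women at up to 90 centers, and inclusion criterion 4 requires a singleton gestation. That is about 200 / 90 = 2.2 infants per center, so few sites will grade enough infants to settle into a common practice.

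**Step 6: effect on the comparison.** Let *p* be the true proportion of infants with a severe event, *Se* the chance that such an infant is recorded as severe, and *Sp* the chance that an infant without one is not. The recorded proportion is *Se* × *p* + (1 − *Sp*) × (1 − *p*). If *Se* and *Sp* are the same in both arms,

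recorded difference = (*Se* + *Sp* − 1) × true difference.

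The multiplier is at most 1, and between 0 and 1 whenever grading is better than chance, so the difference shrinks. If every site read the scale literally, *Se* = 0 and *Sp* = 1, the multiplier is 0 and the severe row is empty. With mixed practice the multiplier lies somewhere above that. The documents give no basis for a value.

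**The case against.** The strongest reply is that the scale is usable for live-born infants. Each level has a treatment part, and words such as usually and generally leave room for judgement. This stands in part: the treatment wording gives a crude ladder that identifies mild events. It does not fix the line between moderate and severe, and it does not help with fetal events. An investigator might also count feeding, say, as an infant's activity, but the protocol does not say so and sites could differ.

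Second, little depends on the table. It is descriptive. Seriousness is judged separately under section 8.10. The IVH component of the primary endpoint is graded by central reading, and NEC has its own definition in Appendix 6. Retinopathy stage, duration of ventilation and respiratory support, NICU stay and status at 36 weeks are recorded apart from the scale. Appendix 4 conditions are collected and reported even when they are not adverse events. All of this stands and limits the point to a cheap improvement. It leaves a gap for events without a grade or stage of their own, such as sepsis, respiratory distress syndrome and events outside Appendix 4.

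Third, section 9 promises a separate SAP, and CRF instructions may exist. Clarification there cannot be ruled out, but investigators assign intensity under the protocol, so a later analysis document alone would not make the grades consistent.

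A reader might also infer three stronger things that the documents do not support:

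- *That site habit would bias the comparison of arms.* Assignment is randomized 1:1 and section 6.4.6 blinds the investigators, so grading habit is unrelated to arm in expectation.
- *That the scale fails equally for mothers.* Bed rest appears in section 4 as background on current practice. Sections 7.2 and 8.2.1 provide for ambulatory subjects, and maternal events are followed to 6 weeks postpartum, when daily activities apply in the ordinary way.
- *That drugs on the Appendix 8 checklist should be disregarded in grading.* The checklist governs how medication is recorded (section 7.8). Starting one of those drugs for a new event can be a real change in care.

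**Conclusion.** The point holds, as a cheap improvement. Section 8.9 applies a stated rule to fetal and infant events whose activity, inconvenience and concern anchors have no meaning for them, and whose treatment anchors separate moderate from severe poorly. Infant intensity in section 9.7 will be graded inconsistently across up to 90 sites, which adds non-differential noise to a descriptive summary supporting secondary objective 2.

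It would go too far to say that the scale cannot be applied to infants at all or that the table carries no information: the treatment wording still separates untreated from treated events. The primary endpoint, seriousness, IVH grade and retinopathy stage are not affected.

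The conclusion assumes that no infant guidance exists in a document outside the text reviewed. The view that the error is noise assumes that blinding holds and that events of similar true severity are treated alike in the two arms. The size of the attenuation cannot be stated from the documents.

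**What to change.** Add a fetal/infant intensity scale to section 8.9, anchored on observable physiological effect and on change in care or support from the infant's own baseline:

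- mild: no change in care or monitoring;
- moderate: minor change in care or monitoring;
- severe: major change in care, life-threatening, or fatal.

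In section 9.7, tabulate infant intensity on this scale, separately from the mothers. The maternal scale can stay as it is.

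If a new scale is not wanted, the minimum is to limit the intensity table to mothers and report infant events by seriousness and, where one exists, by condition-specific grade or stage.

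The cost is a paragraph in section 8.9, matching CRF guidance and site training, plus one regrading from source of any infant events already graded. That regrading should be done blind to treatment. Sample size and the primary analysis do not change.
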